10.3 Appendix 3: Clinical laboratory tests

10.3.1 Clinically notable laboratory values and vital signs

Not applicable.

10.4 Appendix 4: Participant Engagement

The following participant engagement initiatives are included in this study and will be provided, as available, for distribution to study participants at the time points indicated. If compliance is impacted by cultural norms or local laws and regulations, sites may discuss modifications to these requirements with Novartis.

- Thank You letter
- Plain language trial summary - after CSR publication
- Individual study results - after CSR publication

10.5 Appendix 5: Liver safety monitoring

To ensure participant safety and enhance reliability in determining the hepatotoxic potential of an investigational drug, a standardized process for identification, monitoring and evaluation of liver events has to be followed.

Please refer to [Table 10-1](#) in [Section 10.5](#) for complete definitions of liver laboratory triggers.

Once a participant is exposed to study treatment, every liver event defined in [Table 10-1](#) should be followed up by the Investigator or designated personnel at the trial site, as summarized below. Additional details on actions required in case of liver events are outlined in [Table 10-2](#). Repeat liver chemistry tests (i.e., ALT, AST, TBL, PT/INR, ALP and G-GT) to confirm elevation.

- These liver chemistry repeats will be performed using the central laboratory. If results will not be available from the central laboratory, then the repeats can also be performed at a local laboratory to monitor the safety of the participant. If a liver event is subsequently reported, any local liver chemistry tests previously conducted that are associated with this event should have results recorded on the appropriate CRF.
- If the initial elevation is confirmed, close observation of the participant will be initiated, including consideration of treatment interruption if deemed appropriate.
- Discontinuation of the investigational drug (refer to the Discontinuation of study treatment section), if appropriate.
- Hospitalization of the participant if appropriate.
- Causality assessment of the liver event.
- Thorough follow-up of the liver event should include
 - These investigations can include based on Investigator's discretion: serology tests, imaging and pathology assessments, hepatologist's consultancy; obtaining more detailed history of symptoms and prior or concurrent diseases, history of concomitant drug use, exclusion of underlying liver disease.

All follow-up information and procedures performed must be recorded as appropriate in the CRF.

10.5.1 Liver event and laboratory trigger definitions & follow-up requirements

Table 10-1 Liver event and laboratory trigger definitions

Definition/ threshold	
Liver laboratory triggers If ALT, AST and TBIL normal at baseline:	
 • ALT or AST > 5 × ULN • TBIL > 3 × ULN (in the absence of known Gilbert syndrome) • ALT or AST > 3 × ULN and INR > 1.5 • Potential Hy's Law cases (defined as ALT or AST > 3 × ULN and TBIL > 2 × ULN [mainly conjugated fraction] without notable increase in ALP to > 2 × ULN) • Any clinical event of jaundice (or equivalent term) • ALT or AST > 3 × ULN accompanied by (general) malaise, fatigue, abdominal pain, nausea, or vomiting, or rash with eosinophilia • Any AE potentially indicative of a liver toxicity
If ALT or AST abnormal at baseline:	
 • ALT or AST > 3x baseline or > 300 U/L (whichever occurs first)

Table 10-2 Follow up requirements for liver laboratory triggers - ALT, AST, TBL

	ALT	TBL	Liver Symptoms	Action
ALT increase without bilirubin increase:				
	If normal at baseline: ALT > 3 x ULN If elevated at baseline: ALT > 2 x baseline or > 300 U/L (whichever occurs first)	Normal For participants with Gilbert's syndrome: No change in baseline TBL	None	
 • No Action
	If normal at baseline: ALT > 5 x ULN for more than two weeks If elevated at baseline: ALT > 3 x baseline AND >5x ULN for more than two weeks or ALT ≥5x baseline AND ≥8x ULN	Normal For participants with Gilbert's syndrome: No change in baseline TBL	None	
 • Interrupt study treatment • Measure ALT, AST, ALP, GGT, TBIL, INR, albumin, CK, and GLDH in 48-72 hours. • Follow-up for symptoms. • Initiate close monitoring

	ALT	TBL	Liver Symptoms	Action
	If normal at baseline: ALT > 8 x ULN	Normal	None	and workup for competing etiologies.
ALT increase with bilirubin increase:				
	If normal at baseline: ALT > 3 x ULN	TBL > 2 x ULN (or INR > 1.5) For participants with Gilbert's syndrome: Doubling of direct bilirubin	None	
 Study treatment can be restarted only if another etiology is identified and liver enzymes return to baseline.
	If elevated at baseline: ALT > 2 x baseline AND >3x ULN			
	If normal at baseline: ALT > 3 x ULN	Normal or elevated	Severe fatigue, nausea, vomiting, right upper quadrant pain*	
	If elevated at baseline: ALT > 2 x baseline AND >3x ULN			

* This situation suggests liver injury based on (i) elevation of ALT, and (ii) the presence of symptoms of liver injury. Even if bilirubin is normal, the presence of liver symptoms indicates potentially severe liver injury.

Table 10-3 Follow up requirements for liver laboratory triggers - Isolated Hyperbilirubinemia

Criteria	Actions required	Follow-up monitoring
Total Bilirubin (isolated)		
>1.5 – 3.0 ULN	
 • Maintain treatment • Repeat LFTs within 48-72 hours 	Monitor LFTs weekly until resolution to ≤ Grade 1 or to baseline
> 3 - 10 × ULN (in the absence of known Gilbert syndrome)	
 • Interrupt treatment • Repeat LFT within 48-72 hours • Hospitalize if clinically appropriate • Establish causality • Record the AE and contributing factors (e.g., conmeds, med hx, lab) in the appropriate CRF 	Monitor LFTs weekly until resolution to ≤ Grade 1 or to baseline (ALT, AST, TBIL, Alb, PT/INR, ALP and GGT) Test for hemolysis (e.g., reticulocytes, haptoglobin, unconjugated [indirect] bilirubin)
> 10 x ULN	
 • Discontinue the study treatment immediately • Hospitalize the participant • Establish causality • Record the AE and contributing factors (e.g., conmeds, med hx, lab) in the appropriate CRF 	ALT, AST, TBIL, Alb, PT/INR, ALP and GGT until resolution (frequency at Investigator discretion)
Any AE potentially indicative of a liver toxicity	
 • Consider study treatment interruption or discontinuation • Hospitalization if clinically appropriate • Establish causality • Record the AE and contributing factors (e.g., conmeds, med hx, lab) in the appropriate CRF 	Investigator discretion

Based on Investigator’s discretion investigation(s) for contributing factors for the liver event can include: Serology tests, imaging and pathology assessments, hepatologist’s consultancy; obtaining more detailed history of symptoms and prior or concurrent diseases, history of concomitant drug use, exclusion of underlying liver disease.

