18. Major non-cardiac surgical or major endoscopic procedure within the past 6 months prior to the start of screening.
19. Multi-vessel CABG surgery within the past 3 years prior to the start of screening.

20. Planned coronary revascularization (PCI or CABG) or any other major surgical procedure during the study (until EOS).
21. Symptomatic Class IV heart failure (New York Heart Association [NYHA]) at the start of screening.
22. History or current diagnosis of ECG abnormalities indicating significant risk of safety for participants participating in the study such as:
 - Concomitant clinically significant cardiac arrhythmias, e.g., sustained ventricular tachycardia, and clinically significant second or third degree AV block without a pacemaker
 - History of familial long QT syndrome or known family history of Torsades de Pointe
23. Uncontrolled hypertension (defined as systolic blood pressure (SBP) >160 mmHg or diastolic blood pressure (DBP) >100 mmHg) at screening.
24. Uncontrolled diabetes, as defined by the Investigator, at screening. Clinical and laboratory evidence of uncontrolled diabetes may include but are not limited to: hemoglobin A1C >9%, recurrent fasting glucose >200 mg/dL, frequent urination/thirst not explained by other causes, etc.
25. Known nephrotic syndrome diagnosis, or eGFR <30 mL/min calculated using the CKD-EPI formula (https://www.kidney.org/professionals/KDOQI/gfr_calculator), or ≥2+ protein on urine dipstick testing at screening.
26. History of clinically significant liver disease or liver injury at screening as indicated by abnormal liver enzymes or function tests (as defined below) including but not limited to Alanine Aminotransferase (ALT), Aspartate Transaminase (AST), Serum Glutamic Oxaloacetic Transaminase (SGOT), Serum Glutamic Pyruvic Transaminase (SGPT), alkaline phosphatase (ALP), serum bilirubin, albumin and prothrombin time. The Investigator should be guided by the following criteria:
 - Any single parameter may not exceed 2x upper limit of normal (ULN)
27. Uncontrolled asthma at the start of screening, as defined by the Investigator, with high likelihood of requiring systemic corticosteroids during the treatment period.

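### Protocol Tables 10-1, 10-2 and 10-3 disagree on what counts as a liver event in participants whose baseline liver tests are abnormal

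*Protocol*

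**What the plan says.** **Who can enter.** Protocol Section 5.2, criterion 26, names ALT, AST and serum bilirubin among the liver tests and guides the investigator that "Any single parameter may not exceed 2x upper limit of normal (ULN". Mildly abnormal baseline values are therefore allowed.

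**What a liver event is.** Section 10.5 sends the reader to Table 10-1 for the complete trigger definitions and ties follow-up to that table: "Once a participant is exposed to study treatment, every liver event defined in" Table 10-1 is to be followed up by the site. It describes Table 10-2 as further detail on the actions to take when a liver event occurs.

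**Table 10-1** has two rows.
- The first is headed "If ALT, AST and TBIL normal at baseline". It holds the TBIL trigger, the INR trigger ("ALT or AST > 3 × ULN and INR > 1.5"), the potential Hy's Law trigger ("ALT or AST > 3 × ULN and TBIL > 2 × ULN [mainly conjugated fraction", with a further condition on ALP), "Any clinical event of jaundice (or equivalent term", the symptom trigger and the trigger for AEs suggesting liver toxicity.
- The second applies if ALT or AST is abnormal at baseline. It holds one trigger: "ALT or AST > 3x baseline or > 300 U/L (whichever occurs first".

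**Table 10-2** has its own entries for participants with raised baseline ALT. One entry is "If elevated at baseline: ALT > 2 x baseline AND >3x ULN". It appears once beside TBL above 2× ULN or INR above 1.5, and once beside liver symptoms.

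**Table 10-3** sets actions for isolated bilirubin above 1.5× ULN and for any AE suggesting liver toxicity. It sets no condition on baseline ALT, AST or TBIL.

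**The concern.** Section 10.5 is meant to give one standardized process for finding and evaluating liver events. For participants with abnormal baseline tests it gives two answers. A combined rise in ALT and bilirubin can meet an action row in Table 10-2 while the definition table does not call it an event. A participant with only bilirubin abnormal at baseline has no applicable row in Table 10-1.

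What is at stake is consistency between sites. A site that works from the definition table may not open the liver-event follow-up in Section 10.5 (repeat chemistry including PT/INR, event-level causality assessment, CRF recording of the follow-up). A site that works from the action tables will act. The Schedule of Activities adds to this: chemistry is scheduled at every visit, but coagulation only at Screening, Day 1, EOT and EOS. At Days 22, 43 and 64 the INR alternative in Table 10-2 therefore rests on an unscheduled test, which the event follow-up would normally prompt.

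The effect on reporting is smaller. SAP Section 2.7.3 lists, but does not summarize, laboratory data from follow-up of hepatic events. Which participants have such data would depend on which table the site used.

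**Working it through.** There is no figure in the plan to reproduce. The check compares thresholds.

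**Inputs**
- Baseline ALT = b × ULN, with 1 < b ≤ 2 (criterion 26).
- Table 10-2, elevated baseline: ALT above 2× baseline and above 3× ULN, with TBL above 2× ULN, INR above 1.5, or liver symptoms.
- Table 10-1, abnormal ALT/AST: above 3× baseline or above 300 U/L.
- The ULN for ALT is not in the documents. Values of 30 to 55 U/L are assumed, only to place 300 U/L on the ULN scale.

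**Formulas, in multiples of ULN**
- The Table 10-2 row starts above max(2b, 3).
- The Table 10-1 trigger starts above min(3b, 300/ULN).
- ALT between the two, with the bilirubin, INR or symptom finding, meets Table 10-2 but is not a Table 10-1 event. This assumes that AST has not crossed its own Table 10-1 threshold.

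**When 300 U/L matters.** It comes first only if 3b × ULN > 300, that is b > 100/ULN. With b ≤ 2 this needs ULN above 50 U/L. At ULN 55, 300/55 = 5.45.

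| b | Table 10-2 starts above | Table 10-1 starts above | Width |
|---|---|---|---|
| 1.1 | 3.0 | 3.3 | 0.3 |
| 1.25 | 3.0 | 3.75 | 0.75 |
| 1.5 | 3.0 | 4.5 | 1.5 |
| 1.75 | 3.5 | 5.25 | 1.75 |
| 2.0 | 4.0 | 6.0 (5.45 if ULN = 55) | 2.0 (1.45) |

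The band exists for every b above 1, because 3b then exceeds both 2b and 3. It shrinks to nothing as b approaches 1.

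**Worked case.** Baseline ALT 1.6× ULN; on treatment ALT 4.0× ULN and TBL 2.5× ULN.
- Table 10-2: 2 × 1.6 = 3.2 and 4.0 > 3.2; 4.0 > 3; 2.5 > 2. The combined row is met.
- Table 10-1: 3 × 1.6 = 4.8 and 4.0 < 4.8. In U/L, 4.0 × 30 = 120, 4.0 × 40 = 160 and 4.0 × 55 = 220, all below 300. There is no event.

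**Abnormal TBIL only.** With normal ALT and AST and TBIL above 1× and up to 2× ULN at baseline, the first row of Table 10-1 fails on TBIL and the second fails on ALT/AST. No later value meets a row that applies. Table 10-2 branches on baseline ALT alone, so its normal-baseline row (ALT above 3× ULN with TBL above 2× ULN) does apply. For Gilbert's syndrome it uses a doubling of direct bilirubin instead.

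**Isolated bilirubin.** For a participant with abnormal baseline ALT, AST or TBIL, TBIL above 3× ULN without an enzyme trigger draws an action in Table 10-3 (absent known Gilbert syndrome) but is not a Table 10-1 event.

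**The case against.** The strongest reply is that nothing is lost in practice. Tables 10-2 and 10-3 carry their own criteria, and their captions also speak of liver laboratory triggers. Read across its split cell, the Table 10-2 action entry directs interruption, repeat tests in 48–72 hours, monitoring and work-up of other causes for the combined rows. Section 8.4.4 requires every abnormal laboratory result to be assessed as a possible AE, with repeat testing for those that qualify. Section 8.6.1 requires a relationship assessment for each AE, and Section 8.6.3 requires SAE reporting within 24 hours. Section 7.1 leaves room for investigator judgment. Section 10.5 says that Table 10-1 events should be followed up; it does not say that only those events should be.

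Most of this stands, and it rules out some readings that a reader might infer:
- **That these participants get no confirmation, causality assessment or reporting.** The sections above do not depend on Table 10-1.
- **That the gap covers any ALT rise.** Above 3× baseline or 300 U/L, the case is a Table 10-1 event whatever the bilirubin.
- **That the worked case would automatically be a Hy's Law trigger at a normal baseline.** That trigger also requires mainly conjugated bilirubin and no notable ALP rise to above 2× ULN.
- **That these participants are at highest risk, or that Table 10-2 is the correct table.** The documents support neither.

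The reply does not remove the inconsistency. Section 10.5 presents Table 10-1 as complete and Table 10-2 as the actions for events. Table 10-2 then contains elevated-baseline rows that can be met when Table 10-1 declares no event.

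**Conclusion.** The three tables are inconsistent for participants with abnormal baseline liver tests, and the defect is in the liver-event definition and the standardized follow-up tied to it. For abnormal baseline ALT it is a band, from 0.3× ULN wide at b = 1.1 to 2.0× ULN wide at b = 2 (1.45× if ULN is 55 U/L). For abnormal TBIL alone, Table 10-1 has no applicable row.

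This rests on reading the baseline headings in Table 10-1 as governing every bullet beneath them, on the assumed ULN range, and on b staying within the screening limit. The primary analysis is not affected. A safety definition that classifies the same participant in two ways should be corrected.

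**What to change.** Reconcile Tables 10-1, 10-2 and 10-3 so that each baseline category admitted by criterion 26 (all normal; ALT or AST abnormal; TBIL abnormal only) is handled consistently in the event definition and in the action tables. Cover the combined enzyme plus bilirubin or INR pattern, jaundice, symptoms and isolated bilirubin. State in Section 10.5 which table decides that a liver event has occurred. The thresholds, and which table gives way, are for the sponsor's clinical safety team.

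The cost is a table edit through a protocol amendment (Section 10.1.8.1), plus an update of any site or laboratory material built on Table 10-1; the documents do not describe such material. No statistical analysis changes.

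### Some isolated ALT elevations that Table 10-1 makes liver triggers, with follow-up required by Section 10.5, fall in the Table 10-2 row marked No Action

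*Protocol*

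**What the plan says.** Protocol Section 10.5 states a general duty. Once a participant has been exposed, every event defined in Table 10-1 "should be followed up by the Investigator or designated personnel at the trial site, as summarized below". The listed steps begin with "Repeat liver chemistry tests (i.e., ALT, AST, TBL, PT/INR, ALP and G-GT) to confirm elevation" and continue: "If the initial elevation is confirmed, close observation of the participant will be initiated, including consideration of treatment interruption if deemed appropriate". The section refers the reader to Table 10-2 for further detail on the actions required, and Section 7.1 sends investigators to Section 10.5 for liver events.

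Table 10-1 gives the triggers. With normal baseline tests, one trigger is ALT or AST above 5 x ULN. With abnormal baseline ALT or AST, the trigger is "ALT or AST > 3x baseline or > 300 U/L (whichever occurs first").

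Table 10-2 is titled "Follow up requirements for liver laboratory triggers - ALT, AST, TBL". For an ALT rise without a bilirubin rise and without symptoms, it has three steps:

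- **First row, *No Action*.** Normal baseline: ALT above 3 x ULN. Elevated baseline: "If elevated at baseline: ALT > 2 x baseline or > 300 U/L (whichever occurs first").
- **Next row, interrupt treatment, retest in 48-72 hours and monitor closely.** Normal baseline: ALT above 5 x ULN for more than two weeks. Elevated baseline: "ALT > 3 x baseline AND >5x ULN for more than two weeks or ALT ≥5x baseline AND ≥8x ULN".
- **A further row for a normal baseline.** ALT above 8 x ULN, with no duration condition.

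Other rows deal with raised bilirubin or INR, and with liver symptoms. Elevated-baseline participants can enrol, because exclusion criterion 26 says only: "Any single parameter may not exceed 2x upper limit of normal (ULN").

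**The concern.** A value can be a Table 10-1 trigger, and so require repeat chemistry under Section 10.5, while the only Table 10-2 row it meets says *No Action*. Two sites seeing the same ALT result could then handle it differently, although Section 10.5 asks for a standardized process.

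The row above *No Action* also depends on knowing whether an elevation has lasted more than two weeks. A site that takes the first row literally may have no further ALT value until the next scheduled visit. What is at stake is participant safety and uniform handling of liver events. The estimand, the power and the primary analysis are not affected.

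**Working it through.** The plan gives no figure to reproduce. The check applies both tables to the same ALT value, assuming normal bilirubin (or unchanged bilirubin in Gilbert's syndrome) and no symptoms.

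**Rules for an elevated baseline B, with U for the ULN**

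- Table 10-1 trigger: ALT > 3B or ALT > 300 U/L.
- Table 10-2 *No Action*: ALT > 2B or ALT > 300 U/L.
- Table 10-2 interruption: ALT > 3B and > 5U for more than two weeks, or ALT ≥ 5B and ≥ 8U at once.

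**Overlap 1, any ULN.** If 3B < ALT < 5B when first detected, the trigger is met. The immediate limb of the interruption row fails because ALT is below 5B, and the two-week limb cannot yet be met. Only *No Action* remains.

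**Overlap 2, the 300 U/L cut-off.** ALT just above 300 U/L escapes the immediate limb if B > 300/5 = 60 U/L or if U > 300/8 = 37.5 U/L. Taking B as at most 2U (exclusion 26), B > 60 requires U > 30. So:

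- U of 30 or below: no 300 U/L conflict.
- U above 30 and up to 37.5: conflict only for baselines above 60 U/L.
- U above 37.5: conflict at every elevated baseline, for ALT just above 300 U/L.

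The documents give no ALT ULN, so the values of U below are assumptions.

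| Assumed U | B | ALT | ALT/B | ALT/U | Table 10-2 when first detected |
|---|---|---|---|---|---|
| 30 | 60 | 301 | 5.02 | 10.03 | Interruption |
| 33 | 49.5 | 301 | 6.08 | 9.12 | Interruption |
| 33 | 66 | 301 | 4.56 | 9.12 | *No Action* |
| 40 | 80 | 301 | 3.76 | 7.53 | *No Action* |
| 40 | 80 | 350 | 4.38 | 8.75 | *No Action* |
| 40 | 80 | 450 | 5.625 | 11.25 | Interruption |
| 55 | 110 | 301 | 2.74 | 5.47 | *No Action* |

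Every row of the table is a Table 10-1 trigger. In the last row, ALT is below 3B, so it stays at *No Action* even if it persists beyond two weeks.

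**Overlap 3, normal baseline.** ALT > 5U is a Table 10-1 trigger. For 5U < ALT ≤ 8U lasting two weeks or less, neither the two-week row nor the above-8U row is met, so only the above-3U *No Action* row applies. With an assumed U of 40, this is ALT above 200 (5 × 40) and up to 320 U/L (8 × 40).

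**Timing.** The assessment schedule has clinical chemistry on Days 1, 22, 43, 64, 85 and 92. During treatment the gap is 21 days (for example 43 − 22), longer than the 14 days in the persistence condition. Without a repeat test, persistence may not be known until that next visit.

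**The case against.** The best defence is that Section 10.5 sets the minimum for every trigger and Table 10-2 only adds to it, so *No Action* means nothing beyond the Section 10.5 steps, or no change of treatment. This is a possible intention, but the text does not say it. Table 10-2 is titled as follow-up requirements, and its action column contains retesting and monitoring as well as drug decisions. Where the protocol means continuing treatment while retesting, it says so: Table 10-3 tells the site to maintain treatment and repeat the liver tests.

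A second defence is that other provisions limit the gap, and part of this stands. Section 8.4.4 makes repeat evaluation mandatory for laboratory AEs, chemistry is measured at each scheduled visit, and Section 7.1 requires discontinuation for any laboratory abnormality that the investigator judges to prevent continued participation. But the repeat testing in Section 8.4.4 applies only once the result is classed as an AE, and none of these provisions resolves the conflict between the tables.

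A reader might infer more than the documents support:

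- **That every ALT above 300 U/L with an abnormal baseline gets *No Action*.** It does not. Values with raised bilirubin or symptoms are covered by other rows, and values at least 5 times baseline and at least 8 times ULN meet the interruption row at once.
- **That the 300 U/L conflict exists at any plausible ULN.** At an assumed ULN of 30 with a baseline up to 60 U/L, it does not.
- **That the two-week condition can never be judged.** Section 10.5 requires repeat chemistry for triggers, and scheduled chemistry follows about three weeks later. The risk is delay at a site that follows the *No Action* cell.

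**Conclusion.** The inconsistency is real, in the current text, and limited in scope. It concerns isolated ALT elevation without symptoms that does not already meet the interruption row. Within that scope, the conflict between 3 and 5 times baseline (elevated baseline) and the conflict above 5 and up to 8 times ULN for two weeks or less (normal baseline) need no assumed ULN. The 300 U/L conflict does depend on the ULN. It requires a ULN above 30 U/L if baseline is at most 2 x ULN, and it widens as the ULN rises.

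The cap of 2 x ULN is a screening criterion. It is used here as a bound on baseline, which Section 9.2.1 defines as the last value before dosing on Day 1. The link between row and action is read from text extracted from the PDF. *No Action* sits clearly on the first row, but the action cell of the rows below it runs across a page break.

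This is an internal inconsistency in a safety rule that should be corrected. It does not show that any participant would go unmonitored, and it has no effect on the efficacy analysis.

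**What to change.** The sponsor must reconcile the Section 10.5 text, Table 10-1 and Table 10-2 so that each Table 10-1 trigger leads to one consistent instruction. The reconciled text should state how the *No Action* row relates to the follow-up that Section 10.5 requires. Which thresholds and actions apply is for the sponsor to decide, and none is proposed here.

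The cost is a change of protocol wording, made by amendment with the approvals in Section 10.1.8.1. The reconciliation itself calls for no visits beyond what Section 10.5 already requires, and the design, sample size and SAP are unchanged.
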